3. INTRODUCTION AND RATIONALE

One of the main underlying causes of atherosclerotic cardiovascular disease is the retention of LDL-C and other cholesterol containing lipoproteins within the arterial wall. There is an approximately linear relationship between the absolute reduction in LDL-C and the proportional reductions in the incidence of coronary and major vascular events.[1] Clinical trials have clearly shown that the lower the achieved LDL-C values, the lower the risk of future cardiovascular events. Guidelines summarize and evaluate available evidence with the aim of assisting health professionals in proposing the best management strategies for an individual patient with a given condition.[2, 3] For secondary prevention in very-high-risk patients the 2016 ESC Guidelines for the management of dyslipidaemia recommended an LDL-C reduction to <1.8 mmol/l.[1] in the 2019 ESC Guidelines this was narrowed down even further to <50% from baseline and an LDL-C goal of <1.4 mmol/L.[4] If the LDL-C goal is not achieved 4 - 6 weeks after the cardiovascular event (CVE) despite maximal tolerated statin therapy, ezetimibe should be added first, followed by Proprotein convertase subtilisin/kexin type 9 inhibitors (PCSK9-i). [3] The Dutch Cardiovascular Risk Management (CVRM) guideline (in the period PENELOPE was performed) recommends an LDL-C goal of at least <1.8 mmol/L for very high-risk CV-patients.

Adherence to treatment guidelines is a predictor of fewer CV hospitalizations. In real life care, however, compliance to guidelines for secondary prevention of cardiovascular disease, can be improved according to recent European and Swedish national studies. [5-8] A strategy of protocolized, Dutch- and ESC-guideline based stepwise approach in lipid lowering therapy (LLT) to reach target LDL-C in very high-risk patients was studied in the PENELOPE study. Protocolized LLT consisted of 3 steps, with LDL-C levels measured \geq 4 weeks after each step:

- Step 1: if at baseline LDL-C >1.8 mmol/L, then a high intensity statin (HIST), defined as atorvastatin \geq 40 mg OD or rosuvastatin \geq 20 mg OD, had to be initiated.
- Step 2: if \geq 4 weeks after step (1) LDL-C >1.8 mmol/L, then ezetimibe 10 mg OD had to be initiated.
- Step 3: if \geq 4 weeks after step (2) LDL-C >1.8 mmol/L alirocumab had to be initiated following pre-specified criteria:
 - if LDL-C 1.8-2.6 mmol/L, addition and dosing of alirocumab was left at the investigator's discretion

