 - if LDL-C 2.6-3.6 mmol/L, alirocumab 75 mg or 150 mg Q2W had to be initiated (dosing at the investigator's discretion)
 - if LDL-C >3.6 mmol/L, alirocumab 150 mg Q2W had to be initiated.

PENELOPE was designed to demonstrate feasibility and efficacy of guideline-based protocolized LLT in the Netherlands.

PENELOPE-CTRL is designed to document real life LLT and resulting LDL-C target attainment in the Netherlands.

Comparison of PENELOPE and PENELOPE-CTRL will demonstrate whether the strategy of protocolized guideline based LLT results in a higher incidence of target LDL-C levels in secondary prevention at set time points, and quantify this difference.

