8. STUDY OUTCOMES

a. PRIMARY STUDY OUTCOME

The primary outcome is defined as the cumulative incidence of patients reaching the LDL-C target level (≤ 1.8 mmol/L) after admission for a type I (N)STEMI with oral lipid lowering medication only, compared to the designated PENELOPE cohort.

Further details on handling of missing or out of window values collected from regular care will be detailed in the endpoint charter, used for endpoint adjudication.

After analysis of the PENELOPE CTRL data the CTRL cohort will be compared to the original PENELOPE cohort.

b. SECONDARY STUDY OUTCOMES

- a) Mean time of reaching the primary outcome, compared to the designated PENELOPE cohort.
- b) Cumulative incidence of patients reaching the LDL-C target level (≤ 1.8 mmol/L) within 90 days after admission for a type I (N)STEMI with oral lipid lowering medication only. This outcome will be estimated with two analysis:
 - only including patients reaching (at least once) LDL-C target within 90 days (without using LDL-C measurements after this window) and
 - additionally including the first available LDL-C measurement (at least 14 days) after the last modification in oral lipid lowering therapy within 90 days after baseline (even if this measurement is after 90 days). This way CTRL mimics the original PENELOPE dataset, where LDL measurement 4-6 weeks after a drug regimen change was mandatory to establish the treatment effect, and this measurement also includes the effect of the last drug regimen change within 90 days.

- c) Cumulative incidence of patients reaching other LDL-C target levels (e.g. ≤ 1.4 mmol/L and 50% LDL-C reduction compared to baseline) and mean LDL-C levels with only oral medication after admission for a type I (N)STEMI, compared to the designated PENELOPE cohort.
- d) Cumulative incidence of reaching LDL-C target levels (≤ 1.8 mmol/L, ≤ 1.4 mmol/L and 50% LDL-C reduction) compared to baseline) and mean LDL-C levels with any lipid lowering drugs (so including the effects of PCSK9i), compared to the designated PENELOPE cohort.
- e) Cumulative incidence of patients reaching LDL-C target levels with only (i) high-intensive statin (compared to cum. effect after STEP 1 in PENELOPE) or (ii) high-intensive statin and/or ezetimibe (compared to cum. effect after STEP 2 in PENELOPE).

c. STUDY PROCEDURES

As PENELOPE-Control is a retrospective cohort registration there are no study procedures.

d. Randomisation, blinding and treatment allocation

Not applicable.

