10. STATISTICAL ANALYSIS

The primary analysis consists of a comparison of outcomes between de PENELOPE CTRL and the original PENELOPE intention to treat population. Baseline characteristics of the cohorts will be presented. To assess for potential remaining imbalances between the cohorts a t-test and Chi-squared test will be used for continuous and dichotomous variables, respectively.

In case of imbalance in patient characteristics between the cohorts, a step-wise approach will be used to correct for this.

- First, a propensity score is derived to asses for membership of trial. Second, a propensity score is derived on the baseline criteria.
- If the distribution of the propensity scores is dissimilar between PENELOPE CTRL and PENELOPE adjustment for differences in propensity function is done in two methods.
 - First, logistic regression analysis with propensity score as co-variate.
 - Second, stratified analysis with deciles of the propensity score.

Percentages are converted to Odds Ratio to allow for multivariable analysis. Missing values are reported and appropriately imputed in the statistical models.

Statistical analysis will be formalised in the SAP, as well as the statistical methods to be used for endpoint analysis. For comparison between the PENELOPE and PENELOPE CTRL cohort, the same additional exclusion criteria were applied: 'known intolerance for alirocumab' and 'active PCSK9-I therapy at baseline'. Life expectancy <1 year was omitted as this could not be determined reliably from the medical records retrospectively. For the primary outcome and secondary outcomes b, c and e (investigating the effects of oral LLT), patients will be excluded as soon as they start using PCSK9i.

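### Excluding patients when they start a PCSK9 inhibitor removes known oral-therapy failures mainly from PENELOPE, and so inflates its attainment on the primary outcome

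*Protocol*

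**What the plan says.** Protocol section 8 defines the primary outcome as the cumulative incidence of reaching LDL-C ≤1.8 mmol/L "with oral lipid lowering medication only, compared to the designated PENELOPE cohort". Section 10 then states that, for this outcome and for secondary outcomes b, c and e, "patients will be excluded as soon as they start using PCSK9i". The same section takes the comparison group from the "original PENELOPE intention to treat population".

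Section 3 sets out when a PCSK9 inhibitor was started in PENELOPE. At least 4 weeks after ezetimibe was added, with "LDL-C >1.8 mmol/L alirocumab had to be initiated following pre-specified criteria". Between 1.8 and 2.6 mmol/L, "addition and dosing of alirocumab was left at the" investigator's discretion. Above 2.6 mmol/L it was required, and in the highest band "alirocumab 150 mg Q2W had to be initiated".

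The control cohort has no such step. According to section 3, "PENELOPE-CTRL is designed to document real life LLT and resulting LDL-C target attainment in the Netherlands".

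Outcome c also compares "mean LDL-C levels with only oral medication after admission for a type I (N)STEMI, compared to the designated PENELOPE cohort". Only outcome d keeps PCSK9 inhibitor users, and it asks about any lipid-lowering drug.

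**The concern.** In PENELOPE, starting a PCSK9 inhibitor under the step rules means that the patient has just missed 1.8 mmol/L on oral therapy, the same threshold that defines the primary outcome. Excluding starters therefore conditions on a post-baseline event that is almost the outcome itself. The event is triggered by protocol in one cohort and left to routine care in the other. CTRL patients who fail oral therapy mostly remain and count as failures, while many PENELOPE patients who fail disappear.

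The propensity score in section 10 is built on baseline criteria, so it cannot correct a selection made after baseline. Dropping patients by later treatment also sits badly with an intention-to-treat population. For mean LDL-C in outcome c, the PENELOPE patients with the highest values are the ones required to start, so they are the ones who leave.

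The purpose of the study is to quantify the difference between the two strategies. Under this rule it could report a significant advantage for the protocolised strategy even if that strategy achieved nothing more with oral drugs.

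**Working it through.** The protocol states no attainment rate, effect size or power, so there is no figure of its own to reproduce. The size of the bias is shown under stated assumptions.

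**Inputs from the protocol:** PENELOPE comparison cohort N = 663 (section 6a); CTRL 700 to 1200 candidates (section 6d), midpoint 950.

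**Assumed:** true oral attainment p, equal in both cohorts; q = share of oral failures who start a PCSK9 inhibitor (q1 in PENELOPE, q0 in CTRL).

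**1. Starters removed from the denominator**

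Observed attainment = p / (1 − (1 − p)q). The observed odds are p / ((1 − p)(1 − q)), so the spurious odds ratio is (1 − q0)/(1 − q1), whatever p is.

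With p = 0.60, q1 = 0.50, q0 = 0.05:
- PENELOPE: 0.60 / (1 − 0.40 × 0.50) = 0.60/0.80 = 75.0%
- CTRL: 0.60 / (1 − 0.40 × 0.05) = 0.60/0.98 = 61.2%
- Difference 13.8 points; odds ratio 0.95/0.50 = 1.90
- Patients left: 663 × 0.80 = 530 and 950 × 0.98 = 931. The pooled rate is 66.2% and the standard error 2.57 points, so z is about 5.4 and p is below 10⁻⁶.

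Range with q0 = 0.05:
- Smallest (p = 0.80, q1 = 0.25): 0.80/0.95 − 0.80/0.99 = 84.2% − 80.8% = 3.4 points; odds ratio 0.95/0.75 = 1.27
- Largest (p = 0.50, q1 = 0.75): 0.50/0.625 − 0.50/0.975 = 80.0% − 51.3% = 28.7 points; odds ratio 0.95/0.25 = 3.80

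**2. Milder assumptions**

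Let f = (1 − p)q be the share of the whole cohort removed, so that observed attainment is p/(1 − f). The last column is the probability of a two-sided 5% significant result with no true difference, for CTRL n = 700 and n = 1200.

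| p | f PENELOPE | f CTRL | PENELOPE | CTRL | Odds ratio | False significance |
|---|---|---|---|---|---|---|
| 0.70 | 10% | 2% | 77.8% | 71.4% | 1.40 | 0.74 to 0.82 |
| 0.60 | 10% | 2% | 66.7% | 61.2% | 1.27 | 0.53 to 0.61 |
| 0.60 | 5% | 2% | 63.2% | 61.2% | 1.09 | 0.11 to 0.12 |

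**3. Starters censored when they start**

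Suppose 60% attain on the oral steps. The 40% who fail split equally: 20% with high LDL-C start a PCSK9 inhibitor, and 20% with lower LDL-C do not. Assume that, on oral drugs alone, 25% of the lower-LDL-C failures and 5% of the high-LDL-C failures would reach target later.
- Censored estimate: the remaining failures stand in for all failures, 0.60 + 0.40 × 0.25 = 70%
- Attainment had the starters stayed on oral drugs: 0.60 + 0.20 × 0.25 + 0.20 × 0.05 = 66%
- Bias: 4 points in favour of PENELOPE

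If nobody attains later, the censoring bias is nil.

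**4. Starters kept as oral non-attainers**

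The denominator is the full cohort, so in the settings of steps 1 and 2 both cohorts show p: difference 0, odds ratio 1.00.

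**The case against.** The strongest reply is that exclusion at the moment of starting is time-dependent wording. With an outcome called cumulative incidence and a time-to-target secondary outcome, it may mean that oral follow-up simply ends at the start of the PCSK9 inhibitor. Attainment before that point would be kept, and the bias would be nearer the 4 points of step 3 than the 13.8 of step 1. This stands as a point about size. It does not remove the bias, because those censored are known failures with high LDL-C. Section 10 also works with percentages, odds ratios and logistic regression, which need a denominator. The one reading without this bias, that starters count as non-attainers, is not written anywhere, and the sentence excludes patients, not measurements.

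Several limits on the size also stand:
- Starting rates are given for neither cohort. With few starters the bias is about 2 points.
- Alirocumab was optional between 1.8 and 2.6 mmol/L, so not every PENELOPE failure leaves.
- Two oral steps of at least 4 weeks each put step 3 at about 8 weeks or later for a patient who goes through all steps. This limits the effect on the strict 90-day analysis in outcome b.
- The intention-to-treat label may only name the source population, so the conflict there is a tension and not a strict contradiction.

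That the SAP may give details is a weaker reply. The protocol itself fixes the rule and lists the outcomes it governs. Outcome d keeps the starters but answers a different question.

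**Conclusion.** The concern holds and must be fixed, because it affects the primary comparison. The direction follows from the protocol's own rules, provided a larger share of oral failures start a PCSK9 inhibitor in PENELOPE than in CTRL. That is the natural expectation where only one cohort has a protocol trigger. The size cannot be determined from the document. Under removal from the denominator it runs from about 2 points (5% and 2% of the cohorts starting) to 28.7 points (75% and 5% of oral failures starting), with 13.8 points and an odds ratio of 1.90 in the central case. Under censoring the illustrative bias is about 4 points.

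**What to change.** In section 10, replace the exclusion with a rule of this kind: patients who start a PCSK9 inhibitor before reaching the target remain in the analysis and count as not having reached it on oral therapy; in time-to-event form, the start is a competing event and not a censoring time. For mean LDL-C on oral therapy, use the last value before the start. Apply the rule identically in both cohorts to the primary outcome and to outcomes b, c and e, and carry it into the SAP. Outcome d stays as the any-drug comparison. A censoring analysis can be kept as a sensitivity analysis.

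The cost is one sentence in each document. Section 7 already collects start and stop dates in CTRL. For PENELOPE, the abstract describes medication recorded at baseline, three months and one year, so the precision of start dates should be confirmed; the existing rule depends on the same information. The drawback is that a starter who might later have reached target on oral drugs counts as a failure, so the PENELOPE percentage will be less favourable. The sensitivity analysis shows how much that matters.

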11. SAFETY REPORTING

PENELOPE CTRL is a retrospective Registry cohort, collecting data from routine clinical care.

Therefore safety reporting to IRB or RA is not applicable, and is the responsibility of the caregiver as part of routine clinical care.

12. ETHICAL CONSIDERATIONS

a. Regulation statement

In the Netherlands, there is no regulation for non-interventional studies like the Medical Research Involving Human Subjects Act (WMO) for interventional studies. In the absence of a regulation, a

framework of standards (Normenkader) has been put in place to ensure non-interventional studies are properly conducted. These standards aim to provide a framework for those who initiate the study, for those who assess the legitimacy of the study and those who conduct the study. PENELOPE-CRTL will be conducted in accordance with these standards. PENELOPE- CTRL will be used as a control cohort for PENELOPE. PENELOPE is evaluated as a “WMO-obligated” protocol, requiring informed consent. PENELOPE-CTRL is submitted in the DCRF route as a pharma funded investigator initiated nWMO cohort, and evaluated by the MEC-U who also was the central ethic committee for PENELOPE.

b. Recruitment and consent

Retrospective data will be used in this analysis and therefore recruitment and consent are not applicable. Informed Consent has been waived by the MEC_U under the condition that all participating centres have a local opt-out for use of data on the website. This will be documented in the Green Light process before start of data collection.

c. Benefits and risks assessment, group relatedness

Not applicable.

d. Compensation for injury

Not applicable.

13. ADMINISTRATIVE ASPECTS, MONITORING AND PUBLICATION

e. Handling and storage of data and documents

The principal investigator of a study centre is responsible for data capture in CASTOR (eCRF), in which they have access to data of their centre only through personalised accounts. All data are captured in a coded manner, using fake initials and only age at admission, to avoid identification. The key that links patient study ID to EMR records is kept within the hospital by the investigator and his team.

After data base lock, the PI will receive a digital copy of the data entered for his site. All details related to data recording, data handling and data review will be documented in a Data Management Plan.

The principal investigator has the option to outsource the data entry to a centralised person assigned by WCN, if preferred. This professional is kept by professional secrecy and will receive a named account for restricted EMR access.

Study documentation will be kept for 15 years after study closure.

f. Monitoring and Quality Assurance

There will be no monitoring in this retrospective data analysis.

All WCN sites are well trained, have a valid ICH-GCP certificate and use WCN site SOP's.

A Clinical Study Report (CSR) will be sent to all study centres within 10 months following the study's final data transfer.

g. Amendments

Amendments are changes made to the research after a favourable advice from the nWMO advisory committee has been obtained. All amendments to this protocol will be notified to the nWMO advisory committee.

h. Annual Progress Report

Not applicable.

i. Temporary halt and (prematurely) End of Study Report

Not applicable.

j. Public disclosure and publication policy

Results of this study will be published in a peer reviewed medical journal and can be used in future discussions with the Dutch Health Authorities and the Health Insurance Companies.

